1 INTRODUCTION

This statistical analysis plan (SAP) describes the statistical methods to be used during the reporting and analyses of data collected under UCB, Inc. Protocol C87075.

This SAP should be read in conjunction with the study protocol and electronic case report form (eCRF). This version of the plan has been developed using the protocol amendment 5 dated 08Sep2017 and annotated eCRF. Any further changes to the protocol or eCRF may necessitate updates to the SAP.

Following the Food and Drug Administration (FDA) approval of certolizumab pegol (Cimzia®) for Crohn's disease (CD), UCB has committed to collect additional long-term, post-marketing safety data on patients exposed to the product in a real-life setting. To achieve this goal, a pharmacoepidemiologic study entitled SECURE was designed. The study began in January 2009 with the goal of collecting prospective data on 2000 patients prescribed Cimzia and a 2000 patient comparator group prescribed other treatments (including biologics) for CD. At study start, this study anticipated to continue monitoring all enrolled patients for approximately 10 years after enrollment.

The protocol has been amended (Amendment 5) to close enrollment and revise the patient follow-up to 8 years following agreement with the FDA. The decision was based on the results of a 2017 interim analysis that indicated no new safety issues had emerged from the currently known safety profile of Cimzia. Patients who already enrolled in C87075 at the time of stopping enrollment will continue to be followed.

As agreed with FDA in Type C written responses dated 31 July 2020, the SECURE registry study can now be closed. Within the response letter, FDA provided comments and recommendations on the SECURE SAP Amendment 4. The SAP Amendment 5 is updated with consideration to the Agency's feedback.

2 PROTOCOL SUMMARY

2.1 Study objective(s)

2.1.1 Primary objective(s)

The objective of this registry is to measure the safety outcomes among Cimzia patients compared to those that occur while on a different CD treatment regimen.

All SAEs and AEs of interest will be collected and summarized (see Section 8.2.3). All these events represent serious risks known to the class of tumor necrosis factor (TNF) blocking agents. During the clinical development program for CD and rheumatoid arthritis consisting of over 6,000 patients, reported events were consistent with the class.

All analyses are descriptive. No formal hypothesis testing will be conducted.

2.2 Study variable(s)

2.2.1 Primary variable(s)

The primary outcome of this observational study is malignancy (malignant tumors and malignant or unspecified tumors). Additionally, the following safety events will be presented using incidence and event rates, and time-to-event statistics:

- Serious infections
- Opportunistic infections
- Serious cardiovascular events (also called major adverse cardiac events, or MACE)
- Congestive heart failure
- Demyelinating-like disorders
- Aplastic anemia, pancytopenia, thrombocytopenia, neutropenia and leucopenia
- Serious bleeding events
- Lupus and lupus-like illness
- Serious skin reactions

Although not officially AEs of interest, the following events will also be summarized as described in the AEs of Interest – Cimzia Program 2018-06-18 guidance document.

- Hepatic Events
- Hypersensitivity reactions and anaphylactic reactions

Separate from the AEs of interest document, malignant lymphomas, non-melanoma skin cancer, and autoimmune disorders will also be summarized.

2.2.2 Secondary variable(s)

Secondary endpoints include the following:

- Changes in HBI rating scale from baseline to each post-Baseline assessment
- Changes in physician's assessment of disease from baseline to each post-Baseline assessment
- Changes in the patient's disease assessment of disease from Baseline to each post-Baseline assessment

2.3 Study design and conduct

Following protocol amendment 5, this long-term observational study in the USA stopped enrollment with approximately 3045 patients enrolled since study start. From the original study design, approximately half of enrolled patients will be receiving Cimzia for ≤ 12 months or about to receive Cimzia at the time of enrollment. The study will be conducted in all regions in the USA at approximately 280 enrolling investigative sites (community based and academic practice).

Recruitment of Cimzia-treated and comparator patients will be monitored and controlled as needed, and to ensure balanced enrollment over time between both cohorts, recruitment will be matched for disease severity (mild/moderate/severe), age categories and gender.

Patients will be followed for approximately 8 years (reduced from 10 years in protocol amendment 5) during normal physician visits and through direct patient follow-up in the form of web, mail surveys and/or phone follow-up calls. All patients will receive and use their medications according to their normal course of medical treatment per physician clinical judgment.

Follow-up data on the patients will be reported by physicians approximately every six months following enrollment while direct patient follow-up data will be collected quarterly via internet, mail or telephone.

Quarterly progress reports will be generated and sent to the FDA during the patient enrollment period. Subsequently, more detailed yearly informal interim analyses may be conducted to provide updates for regularly scheduled steering committee meetings or to the FDA on the information collected in this study. As agreed with FDA, the study is ending on 28 August 2020, and a single final study report will be submitted in 2021.

2.3.1 Patient Inclusion/Exclusion Criteria

Patients who meet all of the following criteria will be eligible for inclusion into the SECURE Registry:

- Patient (or his/her legally acceptable representative) is able to provide written informed consent to permit collection of data.
- Patient must be 18 years of age or older.
- Patient must have medically documented CD.
- The decision to prescribe Cimzia or other medications has been made by the physician independently of the decision to include the patient in the study.
- Patients participating in randomized, blinded clinical trials for CD or other conditions are not eligible for inclusion into the SECURE registry. Involvement in other registries, where patients follow routine clinical practice, is permitted, however.
- The rules for handling erroneous patient entries are laid out in a separate Analysis Data Reviewers Guide.

Cimzia-treated patients

For a patient to qualify as being treated with Cimzia, they must meet one of the following criteria:

- Patient is receiving treatment with Cimzia for the first time. Patient must receive Cimzia treatment within 2 months of enrollment into the registry.
- Patient is currently receiving treatment with Cimzia for ≤ 12 months. Patients must also receive a Cimzia dose within 2 months following enrollment into the registry.

Comparator patients

Patients enrolled in the comparator group are eligible to participate in the registry if one of the following criteria is fulfilled:

- Patient is switching CD treatments or beginning CD treatment for the first time. Previous Cimzia treatment is prohibited in the comparator group. Patient must receive new CD treatment within 2 months of enrollment into the registry.

- Patient is currently receiving other biologic treatment (excluding Cimzia) for ≤ 12 months. Patient must receive other biologic treatment within 2 months following enrollment into the registry.
- Patient is currently receiving immunosuppressant therapy for ≤ 12 months. Patient must receive immunosuppressant therapy within 2 months following enrollment into the registry.
- Patient is currently receiving systemic steroid therapy for ≤ 12 months. Patient must receive systemic steroid therapy within 2 months following enrollment into the registry.

2.3.2 Schedule of Assessments

No visits are required as part of this protocol. All visits will be scheduled and conducted per standard of care.

Enrolling physicians will complete the baseline data for each patient after enrollment into the study. Although patient care will follow the physician's clinical judgment, it is anticipated that the enrolling physician will see and, therefore, report follow-up data on the patients approximately every 6 months after enrollment (months 6, 12, 18,...). Telephone contacts are permitted every other 6-month period, with the understanding that patients are typically seen by the physician every 12 months at a minimum per usual practice. All data, as described in the protocol are to be collected as available during the telephone contacts.

In an effort to minimize missing data and unreported events patients will directly report data in parallel to the enrolling physician reported data. Direct patient follow-up will occur every 3 months after enrollment (months 3, 6, 9, 12,...) via a web-based system, by mail or phone as requested by the patient. If a patient does not provide the information via the web, mail or phone within approximately 1 week after the 3 month due date, the study patient interview service will call the patient to obtain the required information over the phone. Safety information collected directly from the patient will be available for the study investigative site to review. If 8 consecutive quarterly patient surveys have not been at least partially completed, further attempts at patient contact are not required and the patient is considered lost to follow-up at their last known date.

	Study Entry (Baseline)	Physician- Reported Follow- up ^b	Direct Patient Follow-up
	ENROLLMENT	EVERY 6 MONTHS	EVERY 3 MONTHS
Written informed consent	X		
Assessment of inclusion/exclusion criteria	X		
Demography	X		
Crohn's disease history	X		
Medical and surgical history	X		
Family history	X		
Reason for initiating Cimzia or other medication	X		
Planned Cimzia or other medication treatment period	X	X	
CD treatment medication changes and reason		X	X
Concomitant medications	X	X	X
All SAEs and AEs of interest since time of last completed follow-up ^a		X	
Major changes in health status since last completed follow-up			X
Physician's assessment of disease severity	X	X	
Physician's HBI ^c (see APPENDIX A)	X	X ^e	
Patient's Modified HBI ^d	X		X
Patient's assessment of disease severity	X		X
Reasons for discontinuation from registry (early termination or end of Year 8)		X	

AE=adverse event; CD=Crohn's disease; HBI=Harvey-Bradshaw Index; SAE=serious adverse event

^aAll SAEs and AEs of interest are to be reported through the registry.

^b Telephone contacts are permitted every other 6-month period, with the understanding that patients are typically seen by the physician every 12 months at a minimum per usual practice. No study visits are required as part of this protocol; treating physicians are to manage patients based on clinical judgment and standard of care.

^c This may also be completed by qualified site personnel as designated by the physician.

^d The Modified HBI does not include the abdominal mass question.

^e The Modified HBI is completed during the physician telephone contact instead of the full HBI.

2.4 Determination of sample size

Assuming an 8% annual drop-out rate (1) (withdrawal, lost-to-follow-up or death), approximately 25,000 (12,500 per arm) total patient years (p-y) post-enrollment is expected in this registry. With a two-sided significance level of 0.05, the study is designed to have at least 80% power to detect incidence rate ratios (calculated based on observed rates in the control group) of 1.5 for serious infections, 3.3 for lymphoma, and 1.56 for solid malignancies after 10 years. Event rate estimates for this study were calculated using corresponding event rates observed in a CD anti-TNF α registry study control group (1, 2).

Prior to Amendment 5, the study planned for a total of 4000 patients (2000 patients per arm). A total of 3045 patients (1371 in the Cimzia Cohort and 1674 in the Comparison Cohort) were enrolled as of Mar 2017. The total duration of participation (treatment and follow-up) of 8 years is planned for each patient. At the time of the final analysis, 3076 patients were enrolled in the study.

Prior to Amendment 5, the study planned for a total of 4000 patients (2000 patients per arm). A total of 3045 patients (1371 in the Cimzia Cohort and 1674 in the Comparison Cohort) were enrolled as of Mar 2017. The total duration of participation (treatment and follow-up) of 8 years is planned for each patient. At the time of the final analysis, 3076 patients were enrolled in the study.

3 DATA ANALYSIS CONSIDERATIONS

3.1 General presentation of summaries and analyses

Descriptive statistics will be displayed to provide an overview of the study results. Categorical variables will be summarized by using the number of patients and percentages. The denominator for percentages will be based on the number of patients appropriate for the purpose of analysis. Unless otherwise noted, all percentages will be displayed to 1 decimal place. No percentage will be displayed for zero counts, and no decimal will be presented when the percentage is 100%. Continuous variables will be summarized by using descriptive statistics (n, mean, standard deviation [SD], median, 25th and 75th percentile, and minimum and maximum). All tests will be two-tailed with a Type I error of $\alpha=0.05$. No adjustments for multiple comparisons will be made as all statistical testing will be considered descriptive in nature. All confidence intervals presented will be two-sided. Observed data will be presented to the same number of decimal places as collected. Minimum and maximum will be presented to the same number. Mean, median, coefficient of variance (CV [%]), and any percentiles of interest to 1 extra decimal place and standard deviation to 2 extra decimal places. All of the derivations, summaries, and analyses will be performed by using SAS® Version 9.1.3 or higher. All tables and listings will use Courier New font size 9. Data listings will include all the data collected for all patients in the Enrolled Set (ES). Following FDA approval to close enrollment and reduce the follow-up from 10 years to 8 years, tables will only contain data up to 8 years. Data already collected past year 8 will be listed. A separate Analysis Data Reviewers guide provides guidance for the interpretation of the Analysis Data of C87075. In addition it describes the methods and rules used to reconcile data issues that could not be queried at the sites.

3.2 General study level definitions

Any reference to comparator medication is referring to the 3 medication classes in the eligibility criteria (Corticosteroids, Immunosuppressants or treatment with biologics other than Cimzia) only.

[figure not shown]
3.2.1 Exposure

Cancer progresses in several stages before reaching a detectable, malignant state. While this latency period may differ by cancer type, it is generally believed to occur over a long period of time (3). Thus, a treatment-related event may not be seen until years after the initial exposure. In contrast, acute events typically have very short latency periods; therefore, it is unlikely that a treatment-related event will occur after exposure to the product has ended. For the primary endpoint analysis, 2 different methods of person time calculations will be used, one for malignancy events (Section 3.2.1.1) and one for acute events (Section 3.2.1.2).

3.2.1.1 Person-time at risk calculations for malignancy

Due to the long latency of malignancy, gaps in exposure between treatments will be attributed to the most recent, previous treatment. Gaps in exposure before first known treatment will not be factored into person-time calculations for these events. Any patient exposed to Cimzia during the study will only contribute person-time to the Cimzia cohort from that point onward (Figure 1). As an example, if a malignancy should occur any time after Cimzia exposure (including when Cimzia was known to be used prior to enrollment), it will be attributed to Cimzia. If a malignancy occurred in a patient prior to Cimzia exposure or in a patient with no Cimzia exposure, then it would be attributed to comparator. Thus, a patient may have exposure to multiple comparator drugs, but any malignancies diagnosed after treatment with Cimzia would be systematically attributed to Cimzia, even after ending or switching from Cimzia.

Figure 1: Example person-time at risk for malignancy events

Exposure person-time at risk will be calculated for each CD treatment using the following equation:

$$\text{Last Date} - \text{First Date} + 1$$

where all person-time is contributed to Cimzia after first Cimzia dose is administered.

First date is defined as the latest enrollment date or first CD treatment date after enrollment (whichever is later) or first Cimzia dose date if switching from a comparator treatment after enrollment. Last date is defined as the earliest of the following:

- Date of safety event of interest (for incidence rate calculations only)

- Date of discontinuation, withdrawal, or data cutoff

See Section 11.1, appendix 1 for more examples of treatment allocation scenarios for malignancies.

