11 APPENDICES

11.1 Appendix 1 – Treatment Allocation of Malignancies and Acute Adverse Events

Assumptions:

- Treatment periods described in the dosing column have the drug half-life added to the end of each treatment.
- Overlap is when comparator and Cimzia treatment periods overlap. The overlap can occur during the extended treatment for the drug half-life.
- Abbreviations; IC=Informed Consent Date, EoS= End of Study Date
- Gap and Overlap are not possible treatment groups for Malignancy Time at Risk as per SAP section 3.2.1.1 “Person-time at risk calculations for malignancy”. Overlap would be considered Cimzia and Gap would be assigned to the prior treatment.
- The dosing prior to IC only has an impact on malignancy time at risk. If a subject has no Cimzia dosing prior to IC it is considered to have had Comparator dosing prior to IC regardless of what is recorded in the dosing information.

#	Dosing prior to IC	Dosing during study (IC onwards)	Adverse Event	Treatment AE assigned to	Malignancy Time at Risk		Other AE Time at Risk			
					Cimzia	Comparator	Cimzia	Comparator	Gap	Overlap
1a	No Cimzia	Comparator > Cimzia > Comparator	None	N/A	Start of Cimzia to EoS	IC to Start of Cimzia	Start of Cimzia to Start of Second Period of Comparator	(IC to Start of Cimzia) plus (Start of Second Period of Comparator to EoS)	None	None
1b	Cimzia	Comparator > Cimzia > Comparator	None	N/A	IC to EoS	None	Start of Cimzia to Start of Second Period of Comparator	(IC to Start of Cimzia) plus (Start of Second Period of Comparator to EoS)	None	None

#	Dosing prior to IC	Dosing during study (IC onwards)	Adverse Event	Treatment AE assigned to	Malignancy Time at Risk		Other AE Time at Risk			
					Cimzia	Comparator	Cimzia	Comparator	Gap	Overlap
2a	No Cimzia	Comparator > Cimzia > Comparator	Malignancy during second period of Comparator	Cimzia	Start of Cimzia to Malignancy Start Date	IC to Start of Cimzia	Start of Cimzia to Start of Second Period of Comparator	(IC to Start of Cimzia) plus (Start of Second Period of Comparator to EoS)	None	None
2b	Cimzia	Comparator > Cimzia > Comparator	Malignancy during second period of Comparator	Cimzia	IC to Malignancy Start Date	None	Start of Cimzia to Start of Second Period of Comparator	(IC to Start of Cimzia) plus (Start of Second Period of Comparator to EoS)	None	None

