15a	No Cimzia	Comparator > Gap > Cimzia	First Malignancy during Gap and Second Malignancy during Cimzia	Comparator	None	Start of Comparator to First Malignancy Start Date	Start of Cimzia to End of Cimzia	Start of Comparator to End of Comparator	Start of Gap to End of Gap	None
15b	Cimzia	Comparator > Gap > Cimzia	First Malignancy during Gap and Second Malignancy during Cimzia	Cimzia	IC to Malignancy Start Date	None	Start of Cimzia to End of Cimzia	Start of Comparator to End of Comparator	Start of Gap to End of Gap	None
16a	No Cimzia	Gap > Cimzia	Malignancy during Gap	Comparator	None	IC to Malignancy Start Date	Start of Cimzia to End of Cimzia	None	IC to End of Gap	None

#	Dosing prior to IC	Dosing during study (IC onwards)	Adverse Event	Treatment AE assigned to	Malignancy Time at Risk		Other AE Time at Risk			
					Cimzia	Comparator	Cimzia	Comparator	Gap	Overlap
16b	Cimzia	Gap > Cimzia	Malignancy during Gap	Cimzia	IC to Malignancy Start Date	None	Start of Cimzia to End of Cimzia	None	IC to End of Gap	None
17a	No Cimzia	Gap > Comparator	Malignancy during Gap	Comparator	None	IC to Malignancy Start Date	None	Start of Comparator to End of Comparator	IC to End of Gap	None
17b	Cimzia	Gap > Comparator	Malignancy during Gap	Cimzia	IC to Malignancy Start Date	None	None	Start of Comparator to End of Comparator	IC to End of Gap	None
18a	No Cimzia	Gap > Cimzia	Other AE during Gap	Gap	Start of Cimzia to EoS	IC to Start of Cimzia	None	None	IC to Other AE start date	None
18b	Cimzia	Gap > Cimzia	Other AE during Gap	Gap	IC to EoS	None	None	None	IC to Other AE start date	None
19a	No Cimzia	Gap only i.e. no evidence of Comparator or Cimzia dosing	Malignancy during Gap	Comparator	None	IC to Malignancy Start Date	None	None	IC to EoS	None

#	Dosing prior to IC	Dosing during study (IC onwards)	Adverse Event	Treatment AE assigned to	Malignancy Time at Risk		Other AE Time at Risk			
					Cimzia	Comparator	Cimzia	Comparator	Gap	Overlap
19b	Cimzia	Gap only i.e. no evidence of Comparator or Cimzia dosing	Malignancy during Gap	Cimzia	IC to Malignancy Start Date	None	None	None	IC to EoS	None
20a	No Cimzia	Gap only i.e. no evidence of Comparator or Cimzia dosing	Other AE during Gap	Gap	None	IC to EoS	None	None	IC to Start of Other AE start date	None
20b	Cimzia	Gap only i.e. no evidence of Comparator or Cimzia dosing	Other AE during Gap	Gap	IC to EoS	None	None	None	IC to Start of Other AE start date	None

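### For malignancy, SAP 3.2.1.1 and Appendix 1 start person-time on different dates when follow-up opens with a treatment gap

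*SAP*

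**What the plan says.** SAP 3.2.1.1 (malignancy person-time):
- On gaps: time between treatments goes to the preceding treatment, but "Gaps in exposure before first known treatment will not be factored into person-time calculations for these events".
- On the start of the clock: "First date is defined as the latest enrollment date or first CD treatment date after enrollment (whichever is later"). A later start applies to Cimzia person-time after a switch from comparator.
- On attribution to Cimzia: a malignancy at any time after Cimzia exposure counts ("including when Cimzia was known to be used prior to enrollment), it will be attributed to Cimzia").
- On attribution to comparator: for a malignancy before Cimzia, or "in a patient with no Cimzia exposure, then it would be attributed to comparator".

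SAP 11.1, Appendix 1:
- On a patient without Cimzia before consent, the assumptions say "it is considered to have had Comparator dosing prior to IC regardless of what is recorded in the dosing information". A Gap goes to the prior treatment.
- Rows 16a to 20a (no prior Cimzia, Gap first) run Comparator time from consent. Row 18a gives "IC to Start of Cimzia" although the only study drug is Cimzia.
- Rows 16b to 20b (prior Cimzia) run Cimzia time from consent.
- Rows 19a to 20b cover "Gap only i.e. no evidence of Comparator or Cimzia dosing".

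SAP 8.1.3 measures malignancy time from first exposure and refers back to 3.2.1.1. It does not say whether exposure before enrollment counts as first.

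**The concern.** The interval from consent to the first post-enrollment dose is part of the time origin for the primary outcome's incidence rate and hazard ratio. A programmer working from the First Date definition leaves it out; one working from Appendix 1 puts it in. Both would be following the SAP. Section 3.2.1.1 is also at odds with itself: its attribution sentences count a malignancy in that interval, while its start date gives the event no usable person-time. SAP 12.5 says Amendment 5 was meant to make time at risk consistent between the time-to-event and the exposure-adjusted incidence analyses. That aim is not met for malignancy while its time at risk has two definitions.

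**Working it through.** **Step 1. Which sentences conflict, and for whom**

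| Patient with a leading Gap | Gap sentence vs Appendix 1 | First Date vs Appendix 1 | Arm of a malignancy in the Gap |
|---|---|---|---|
| Recorded prior Cimzia (rows 16b-20b) | agree | disagree | Cimzia in both |
| Recorded prior comparator ('a' rows) | agree | disagree | Comparator in both |
| Neither recorded ('a' rows) | disagree | disagree | Comparator in both |

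In the first two lines the Gap follows a known treatment, so the between-treatments rule of 3.2.1.1 gives the Appendix result. In the third line no known treatment exists. The Appendix supplies one by assumption, which cannot be true of everyone: SAP 2.3.1 admits comparator patients under "Patient is switching CD treatments or beginning CD treatment for the first time". If a deemed treatment counted as known, every patient would have a prior treatment and the exclusion sentence could never operate.

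**Step 2. One patient through both rules**

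Take consent (treated as the enrollment date) as day 1, first post-enrollment dose on day 61 and malignancy on day 31 (rows 16a, 16b, 17a, 17b). The SAP formula is Last Date - First Date + 1.
- Section 3.2.1.1: 31 - 61 + 1 = -29 days.
- Appendix 1: 31 - 1 + 1 = 31 days.

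Row 18a with the same dates: 0 Comparator days under First Date, about 60 under the Appendix. Row 20a: First Date does not exist, while the Appendix counts the whole follow-up.

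**Step 3. Size, on assumptions**

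The SAP has no figure to reproduce. Inputs from the documents: 1674 Comparison and 1371 Cimzia patients, 8% annual drop-out, 8 years (SAP 2.4); first dose due within 2 months (SAP 2.3.1). Assumed: no switching, and 25% to 100% of patients in 'a' rows with a leading Gap of 1 to 2 months (30.4 to 60.9 days).

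Person-years per patient = (1 - 0.92^8)/(-ln 0.92) = 5.838. Comparator base = 1674 x 5.838 = 9,773 p-y.

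The Appendix adds the Cimzia cohort's leading Gaps to that base; First Date removes the Comparison cohort's.
- 25% of patients, 1 month: 9,773 + 28.5 = 9,801 against 9,773 - 34.8 = 9,738; ratio 1.0065.
- 50%, 1 month: 9,830 against 9,703; ratio 1.013.
- 100%, 2 months: 9,773 + 228.6 = 10,001 against 9,773 - 279.1 = 9,494; ratio 1.053.

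The study ended on 28 August 2020, so patients enrolled after August 2012 could not reach 8 years. With 6 or 4 years for everyone (4.721 or 3.401 p-y each) the 50%, 1-month case gives 1.6% or 2.2%, and the 100%, 2-month case 6.7% or 9.4%.

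The largest 8-year case moves about 508 p-y. At assumed rates of 0.3, 0.5 and 1.0 malignancies per 100 p-y, that time would hold 1.5, 2.5 and 5.1 events.

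Gap-only patients come on top. If they were 1% to 5% of 1674 (assumed), the Appendix would count 98 to 489 p-y for them, and First Date none.

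**The case against.** The strongest reply is that Appendix 1 already answers these cases. Section 3.2.1.1 points to it for further examples, and the Appendix cites 3.2.1.1 as its basis. The patient with -29 days is worked out in rows 16 and 17, so First Date needs only a wording correction. This largely stands for patients with a recorded prior drug. It does not stand for the rest, because the Appendix rests there on dosing deemed against the record.

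The reply on size also has force. All analyses are descriptive. At an assumed 0.5 per 100 p-y, 9,773 Comparator p-y would yield about 49 events, with a 95% interval of roughly +/-1.96/sqrt(49) = 28%. The upper cases in the working put every patient in an 'a' row. Yet patients already on Cimzia fall in 'b' rows, and Appendix 1 extends each treatment period by the class half-life (70 days for biologics), so many patients on a biologic at entry may have no leading Gap.

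A reader might infer more than this. One inference is that the two texts put early malignancies in different arms; they do not. Another is that the rate ratio shifts in a known direction. With events unchanged, the Appendix lowers the Comparator rate, but if events before First Date are dropped the direction depends on where they fall. A third is that the upper percentages size the conflict with the gap sentence. They do not, because the documents give no count of patients with neither drug on record.

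**Conclusion.** The contradiction is real and concerns the primary outcome, but it is a conflict of person-time and not of arm attribution. First Date disagrees with all of rows 16a to 20b; the gap sentence disagrees only for patients with neither Cimzia nor a comparator on record before consent. Followed literally, 3.2.1.1 counts some malignancies that have zero or negative person-time.

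The size cannot be derived from the documents. In the Full Analysis Set, where the 2-month dosing criterion limits the Gap, it is probably a few percent or less of Comparator person-time; that is a judgement from assumed ranges. Rows 19a and 20a are different in kind, because there the Gap is the whole follow-up. Such patients fail the dosing criterion, so they matter mainly in the Enrolled Set analyses, where that limit does not apply. Sections 3.6 and 8.2.2 do not settle the matter: one dates study-emergence from consent, the other from the first dose after enrollment. Severity: minor to should-fix.

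**What to change.** Choose one rule for the interval from consent to the first post-enrollment dose, and for patients with no dosing. Use it in the First Date definition, the gap sentence, 8.1.3 and Appendix 1, so that every counted malignancy has matching person-time.

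1. The simplest edit starts First Date at enrollment/consent and assigns the leading Gap as the attribution sentences and Appendix 1 already do. The gap sentence is reworded to match, and the deemed comparator use is stated in 3.2.1.1 as a convention. This leaves the attribution rule of Protocol 6.4.1.1 and the two malignancy groups of SAP 3.6 untouched.
2. As a sensitivity analysis, start at the first recorded post-enrollment treatment and drop leading-Gap time and events from both numerator and denominator. This shows how far the result depends on the convention.
3. Tabulate patients, person-years and malignancies in leading Gaps and in gap-only patients, by recorded prior Cimzia, prior comparator, or neither. The last category also takes patients whose only earlier Crohn's drug lies outside the three comparator classes of SAP 3.2.

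Cost: text edits, one re-derived date, one sensitivity table and one count table. No new data are needed.
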